11. ADVERSE EVENTS

11.1. Monitoring, Recording and Reporting of Adverse Events

An AE is any noxious, unintended, or untoward medical occurrence that may appear or worsen in a subject during the course of a study. It may be a new intercurrent illness, a worsening concomitant illness, an injury, or any concomitant impairment of the subject's health, including laboratory test values (as specified by the criteria below), regardless of etiology. Any worsening (ie, any clinically significant adverse change in the frequency or intensity of a pre-existing condition including AML relapse) should be considered an AE. A diagnosis or syndrome should be recorded on the AE page of the CRF rather than the individual signs or symptoms of the diagnosis or syndrome.

An overdose, accidental or intentional, whether or not it is associated with an AE, or abuse, withdrawal, sensitivity or toxicity to an IP should be reported as an AE. If an overdose is associated with an AE, the overdose and AE should be reported as separate terms.

All subjects will be monitored for AEs during the study. Assessments may include monitoring of any or all of the following parameters: the subject's clinical symptoms, laboratory, pathological, radiological or surgical findings, physical examination findings, or other appropriate tests and procedures.

All AEs will be recorded by the Investigator from the time the subject signs informed consent to 28 days after the last dose of IP or until the last study visit, whichever period is longer. Adverse events and SAEs will be recorded on the AE page of the CRF and in the subject's source documents. All SAEs must be reported to Celgene Drug Safety within 24 hours of the investigator's knowledge of the event by facsimile, or other appropriate method, using the SAE Report Form, or approved equivalent form. Please note that SPMs will be monitored as events of interest throughout the duration of the study including post treatment follow-up period and must be reported as SAEs regardless of the treatment arm the subject is in.

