11.5. Reporting of Serious Adverse Events

Any AE that meets any criterion for an SAE requires the completion of an SAE Report Form in addition to being recorded on the AE page/screen of the CRF. All SAEs must be reported to Celgene Drug Safety within 24 hours of the investigator's knowledge of the event by facsimile, or other appropriate method, using the SAE Report Form, or approved equivalent form. This instruction pertains to initial SAE reports as well as any follow-up reports.

Development of SPMs will be monitored as events of interest throughout the duration of the study including the post treatment follow-up period and must be reported as SAEs regardless of the treatment arm the subject is in. This includes any SPM, regardless of causal relationship to IP (oral azacitidine or placebo), occurring at any time for the duration of the study, from the time of signing the ICD until death, lost to follow-up, withdrawal of consent for further data collection, or study closure. Events of SPM are to be reported using the SAE report form and must be considered an "Important Medical Event" even if no other serious criteria apply; these events must also be documented in the appropriate page(s) of the CRF, ie, AE and SPM and subject's source documents. Documentation on the diagnosis of progression to AML and/or the SPM must be provided at the time of reporting as an SAE (eg, any confirmatory histology or cytology results, X-rays, computed tomography [CT] scans, etc.).

The investigator is required to ensure that the data on these forms are accurate and consistent. This requirement applies to all SAEs (regardless of relationship to IP) that occur during the study (from the time the subject signs informed consent to 28 days after the last dose of IP or until the last study visit, whichever period is longer), and those made known to the investigator at anytime thereafter that are suspected of being related to IP. Serious AEs occurring prior to treatment but after informed consent will be collected.

The SAE report should provide a detailed description of the SAE and include a summary of hospital records and other relevant documents. If a subject died and an autopsy has been performed, copies of the autopsy report and death certificate are to be sent to Celgene Drug Safety as soon as these become available. Any follow-up data will be detailed in a subsequent SAE Report Form, or approved equivalent form, and sent to Celgene Drug Safety.

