### **Time to discontinuation from treatment**

Time to discontinuation from treatment will be assessed and is defined as the interval from the date of randomization to the date of discontinuation from IP. Subjects who are ongoing in treatment at the time of study closure will be censored at the date of last visit.

Time to discontinuation from treatment will be analyzed using a competing risk model with reason for treatment discontinuation classified as:

- Disease relapse
- Adverse event(s)
- Became eligible for bone marrow or stem cell transplant
- Withdrawal of consent / lost to follow-up / protocol violation /Other
- Death

Cumulative incidence curves will be estimated and summarized for each specific reason for discontinuation from treatment by treatment arm.

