### 12.1. Adverse Events

Adverse events (AEs) will be coded according to MedDRA, version 22. The severity of AEs will be assessed by the investigator according to the Common Terminology Criteria for Adverse Events (CTCAE) version 4.0. For any AE not listed in the CTCAE grading system, the severity of these events will be assessed by the Investigator using a 5-point scale: “Grade 1/Mild,” “Grade 2/Moderate,” “Grade 3/Severe,” “Grade 4/Life-threatening,” or “Grade 5/Death.” TEAEs with a missing severity will be presented in the summary table as a severity category of “Missing.” Relationship of AEs to investigational product by the investigator is documented on the eCRF. Adverse events that are missing the relationship to study medication will be presented in the summary table as “treatment-related”. The imputed values for relationship to study drug will be used for incidence summaries while actual values will be presented in data listings.

Treatment-emergent adverse events (TEAEs) include adverse events that started between the first dose date and 28 days after the last dose date of study treatment. Alternative definition of TEAEs will also be defined from first dose date to 28 days after the last dose date of study treatment, or date of start of subsequent AML therapy, whichever is earlier. This definition is employed to better differentiate the incidence of TEAEs between oral azacitidine and placebo without potential attenuation of differences due to events that occur in both arms due to subsequent therapies (that may have initiated prior to 28 days post last dose of study treatment).

Adverse events will be summarized by system organ class, preferred term, and treatment arm. Adverse event summaries will include frequency tables of:

- Summary of TEAEs;
- TEAEs;
- TEAEs by decreasing order of frequency of PT;
- TEAEs by decreasing order of frequency of system organ class;
- TEAEs with most frequent preferred terms ( $\geq 10\%$  in the oral azacitidine group);
- Any occurrence of TEAEs by cycle of onset;

- Any occurrence of TEAEs by cycle day of onset;
- First occurrence of TEAEs by cycle of onset;
- First occurrence of TEAEs by cycle day of onset;
- TEAEs by maximum severity;
- TEAEs with severity of grade 3 or 4;
- TEAE with severity of grade 1 or 2;
- TEAEs leading to death;
- TEAEs related to study medication;
- TEAEs related to study medication with severity of grade 3 or 4;
- TEAEs related to study medication leading to death;
- serious TEAEs;

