- serious TEAEs by decreasing order of frequency of PT;
- serious TEAEs related to study medication;
- serious TEAEs with severity of grade 3 or 4;
- serious TEAEs related to study medication with severity of grade 3 or 4;
- TEAEs leading to study medication discontinuation;
- TEAEs leading to dose reduction of study medication;
- TEAEs leading to dose interruption of study medication;
- TEAEs leading to dose interruption and reduction of study medication;
- TEAEs by sex;
- TEAEs by age group (< 65, ≥ 65 to 75, and ≥ 75years);
- TEAEs by race group (White, Asian, Black or Others);
- TEAEs by ECOG performance status (0 or 1, 2 or 3)

Additionally, the incidence rate per 100 person-years will be summarized for all TEAEs and Grade 3 or 4 TEAEs by system organ class, preferred term, and treatment arm. The incidence rate per 100 person-years is calculated as  $(100*n)/T$ , where n is the number of subjects with the given AE at the system organ class or preferred term level, and T is total person-years of exposure. If a subject has multiple events with the same preferred term, then the time to the first event is used. For subject with no event, time to earlier of last dose + 28 days or death date is used.

Subjects with multiple events reported for the same preferred term will be counted only once per system organ class and preferred term level. For summaries by severity (CTCAE grade), subjects with multiple events at the preferred term level will be counted once and for the highest reported severity. For summaries by treatment cycle, subjects with multiple events reported with

a start date within the same cycle for the same preferred term will be counted once per system organ class level and preferred term level within the cycle.

In summaries of TEAEs related to study medication, if a subject reports multiple occurrences of the same AE, only the related occurrence will be summarized. Adverse events with missing relationship to study medication will be imputed as related to study medication.

Additional safety analysis may be performed, displayed and summarized, when deemed necessary.

To assess the safety profile among subjects who have dose escalation, defined as subjects who have at least one assigned dose of 300mg × 21/28 days, the following summary tables will be provided in subjects with dose escalation:

- First occurrence of TEAE by dose schedule period (300mg × 14/28days, 300mg × 21/28days);

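### AML relapse is an adverse event under the protocol and stays in the pooled TEAE rows, where it can dilute a between-arm toxicity difference

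*SAP*

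**What the plan says.** Protocol 11.1 counts as an adverse event "any clinically significant adverse change in the frequency or intensity of a pre-existing condition including AML relapse". On collection it says "All AEs will be recorded by the Investigator from the time the subject signs informed consent", and recording continues to at least 28 days after the last dose.

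SAP 12.1 defines TEAEs as "adverse events that started between the first dose date and 28 days after the last dose date of study treatment". The listed tables use that set: overall summary, grade 3 or 4, serious, fatal, and "TEAEs leading to study medication discontinuation", among others. Rates per 100 person-years are planned for all TEAEs and for grade 3 or 4 TEAEs, by system organ class and preferred term. No visible text in SAP 12 to 12.3, or in the list of changes in SAP 15, removes relapse or progression terms or plans a version without them.

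SAP 12.1 also gives an alternative TEAE definition that ends at subsequent AML therapy if that comes before the 28-day limit. Its purpose is to compare the arms "without potential attenuation of differences due to events that occur in both arms due to subsequent therapies".

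SAP 4.2.2 makes documented relapse a component of RFS, the key secondary efficacy endpoint.

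**The concern.** Safety and tolerability is a secondary objective, and pooled any-event rows are a usual first look at it. If they count relapse, they mix toxicity with a failure of efficacy. The mixing has a direction: a drug that delays relapse adds fewer relapse events to its own arm than placebo does, so a true excess of toxicity looks smaller.

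Subjects are counted once per row, so the relapse row cannot simply be subtracted from a pooled row. The SAP already treats this kind of attenuation as worth a second analysis when subsequent therapy causes it. Relapse normally comes before that therapy and is left in both definitions.

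**Working it through.** **Step 1: does relapse fall in the window?** Under Protocol 12, relapse above 15% blasts ends treatment, so its onset lies close to the last dose. Under Protocol 8.2.6, a subject with blasts above 5% and up to 15% may stay on study drug, so that onset is on treatment. Relapses first found later in follow-up (Protocol 6.14) can fall outside the window. Relapse during treatment is therefore in, and later relapse often is not.

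**Step 2: which rows can it enter?**

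| Row | Condition for a relapse to count |
|---|---|
| Any TEAE | Recorded as an AE, onset in the window |
| Grade 3 or 4 | Also given that grade (a fatal event is grade 5, Protocol 11.2.2) |
| Serious | Also meets a criterion in Protocol 11.2.1; relapse is not on the list of exempt hospitalizations |
| Leading to death | Relapse event is fatal |
| Leading to discontinuation | Recorded as an AE that led to stopping study drug |
| System organ class holding the relapse term, and its exposure-adjusted rate | As for any TEAE, or for grade 3 or 4 |

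The alternative definition changes none of this for a relapse that starts before subsequent therapy.

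**Step 3: illustration of size.** The documents give no toxicity rate, no rate of relapse recorded as an AE, and no figure for the safety comparison. The only effect size they give is the OS hazard ratio of 0.70 (SAP 4.4). It reproduces: 4 × (1.960 + 1.282)² / (ln 0.70)² ≈ 330.4, rounded up to 331 deaths, against 330 stated. The point does not depend on it. I borrow 0.70 as an assumed hazard ratio for relapse in the window.

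Let t be the proportion with a non-relapse event in the row and r the proportion with relapse counted in it. If the two are independent:

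- row proportion = 1 − (1 − t)(1 − r)
- r(aza) = 1 − (1 − r(pbo))^0.70

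Assume t = 30% for azacitidine and 20% for placebo, a true excess of 10 points.

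| r placebo | r azacitidine | Row, placebo | Row, azacitidine | Difference (points) |
|---|---|---|---|---|
| 0% | 0% | 20.0% | 30.0% | +10.0 |
| 10% | 7.1% | 28.0% | 35.0% | +7.0 |
| 20% | 14.5% | 36.0% | 40.1% | +4.1 |
| 30% | 22.1% | 44.0% | 45.5% | +1.5 |
| 50% | 38.4% | 60.0% | 56.9% | −3.1 |

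The difference is zero where (1 − r(pbo))^0.30 = 0.70/0.80, which gives r(pbo) = 1 − 0.875^(1/0.30) ≈ 36%.

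**Step 4: sensitivity.**
- Other toxicity rates: the zero point moves to about 40% for 40% versus 30%, and about 70% for 65% versus 50%.
- Relapse hazard ratio, at 30% placebo relapse and 30% versus 20% toxicity: 0.6, 0.7, 0.8 and 1.0 give −0.5, +1.5, +3.4 and +7.0 points. Equal relapse also shrinks the absolute difference.
- Dependence: with the greatest possible overlap, a row equals the larger of t and r. At 10% placebo relapse the row shows 30% versus 20%, so nothing is lost. At 30% it shows max(30, 22.1) = 30% versus max(20, 30) = 30%, a difference of zero. Overlap can remove the distortion or leave it in place.

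**The case against.** The strongest reply is that the plan has many outputs that relapse does not touch. SAP 12.1 tabulates TEAEs by preferred term and gives separate drug-related tables. SAP 12.2.1 covers events of special interest, and relapse is not a category there. SAP 12.4 gives laboratory shifts by CTCAE grade. SAP 12.3 splits deaths by investigator category and coded cause. SAP 12 commits to by-subject listings of the serious, grade 3 or 4, fatal and discontinuation sets, from which the overlap could be worked out by hand. All of this stands. A reader might infer that azacitidine toxicity would be hidden, but the documents do not support that. The drug-related tables are only largely protected, because SAP 12.1 counts a missing relationship as related.

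It is also fair that not every relapse enters every row (Step 2), and that Step 3 rests on assumed rates. A reader might take the Protocol 11.5 sentence "Documentation on the diagnosis of progression to AML and/or the SPM must be provided at the time of reporting as an SAE" to mean that relapse is always a serious event. It stands in the paragraph on second primary malignancies and concerns paperwork. It does not make relapse serious by rule.

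A reader might further infer that the time-to-discontinuation analysis in SAP 11.3.2 double counts, because a subject stopped for relapse could fit both the relapse and the adverse-event cause. The documents largely answer this. Protocol 10.5 summarises one primary reason, SAP 6 takes reasons from the CRF with disease relapse as its own category, and Protocol 12 defines that category by blast criteria. The separate category does not, however, take relapse out of the TEAE table for discontinuation.

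Finally, all-inclusive tables follow from the protocol's AE definition, and the alternative TEAE window has a different stated purpose, so leaving relapse in it is not a contradiction. SAP 12.1 allows additional safety analyses, but that clause is optional and names no relapse exclusion.

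**Conclusion.** The point holds for the pooled TEAE rows, and for the system organ class row that holds the relapse term with its exposure-adjusted rate. Those rows can contain a component of RFS. If azacitidine delays relapse, a between-arm toxicity difference in them can be diluted. The size cannot be known from the documents. It depends on how often relapse is recorded as an AE in the window, how far that differs between arms, and how much it overlaps with other events. Under the stated assumptions a 10-point excess falls to between 7.0 and 1.5 points as placebo relapse goes from 10% to 30%, and reverses only above about 36%. Nothing in the documents shows that relapse would be recorded that often in the serious or grade 3 or 4 rows, so the reversal should not be read as a forecast.

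A reader might also conclude that the relapse-excluded rows should become the main safety comparison. The documents give no basis for that. The all-inclusive rows are the protocol-defined ones, and an excluded version depends on the choice of terms.

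**What to change.** Before unblinding, add to SAP 12.1 a prespecified list of MedDRA terms for relapse or progression of the studied AML. Repeat five pooled summaries without those terms: overall, grade 3 or 4, serious, leading to death, and leading to discontinuation. Present them as companion tables beside the unchanged all-inclusive tables.

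The cost is a term list to agree and a few more tables. No new data are needed. AE collection, expedited reporting and the time-to-discontinuation analysis stay as they are. Fixing the list in advance matters because terms chosen after the arms are known would be less credible.

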10.7. Safety Analysis

All safety analyses will be performed on the safety population.

Adverse Events will be coded using MedDRA. Adverse event listings will include the verbatim term and the MedDRA preferred term. Treatment-emergent AEs (TEAEs) will be summarized by worst severity grade, system organ class, and preferred term. Treatment-emergent AEs leading to death or to discontinuation from treatment, AEs classified as CTCAE (Version 4.0) Grade 3 or Grade 4, AEs related to IP, and SAEs will be summarized separately. Time to discontinuation from the study due to AE will be summarized using KM methods. Listings of all deaths and all SAEs, regardless of when they occurred, will also be generated. Development of a SPM will be documented as an SAE (considered to be at least an “important medical event” even if no other seriousness criteria apply) throughout a subject’s duration in the study (signing of ICD through the follow-up period of the study).

Clinical laboratory results will be summarized descriptively by treatment group, which will also include a display of change from baseline. Laboratory values outside of the normal ranges will be identified. Clinically significant hematologic and non-hematologic laboratory abnormalities that meet Grade 3 or Grade 4 criteria according to the CTCAE will be listed and summarized. Graphical display of select laboratory parameters over the course of the study will be provided.

Vital sign measurements and ECOG performance status will be listed for each subject at each visit. Descriptive statistics for the vital signs and ECOG performance status, both observed values and changes from baseline, will be summarized by treatment group.

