### **11.2.1. Primary Efficacy Analysis**

The primary efficacy analysis will be performed using the ITT population. The null hypothesis for testing the primary efficacy endpoint, time to death from any cause, is that the overall survival distributions for the oral azacitidine and placebo groups are equivalent. The analysis of the primary efficacy endpoint will be conducted using a stratified log-rank test, stratifying by age at time of induction therapy, prior history of MDS, cytogenetic risk category, received consolidation therapy following induction therapy. The p-value from the stratified log-rank test will be the p-value for primary analysis. The p-value from unstratified log-rank test will also be

provided. The KM method will be used to estimate the survival distribution functions for each treatment arm. KM estimates for median OS as well as the 25th and 75th percentiles and associated two-sided 95% CIs will be summarized for each treatment arm. In addition, the numerical difference, and 95% CI of the difference, in the median, 25th, and 75th percentiles between the two treatment arms will be presented. Plots of the KM survival curves will be presented for the two treatment arms, unadjusted for the stratification variables. A stratified Cox proportional hazards model will be used to estimate the hazard rate ratio and the corresponding 95% CI for oral azacitidine relative to placebo.

Additionally, KM methods will be used to estimate the 1-year and 2-year survival probabilities for time to death from any cause. Estimates of the 1-year (365 days) and 2-year (730 days) survival probabilities and corresponding 95% confidence intervals will be presented by treatment arm. Kaplan Meier methods will also be used to estimate the death probabilities at 30, 90 days, 6 months and 1 year. The death rate (count and percent) at 30, 90 days, 6 months and 1 year will also be summarized.

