### **12.3. Death**

The primary cause of death verbatim term as recorded on the CRF death form will be coded according to MedDRA, version 22. The CRF death form also collects the Primary Category of Death Cause, as selected by the investigator. A summary of all deaths will be provided by treatment period, primary category of death cause by investigator, and the coded primary cause of death (by system organ class, preferred term).

An additional summary of death will be provided for ITT population.

Listings will be provided and will include all subjects who died after signing informed consent.

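### SAP 12.1 plans person-year rates for all TEAEs and Grade 3 or 4 TEAEs but only crude percentages for serious TEAEs, which depend on exposure if it differs by arm

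*SAP*

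**What the plan says.** SAP 12.1 opens its list of adverse event tables with "Adverse event summaries will include frequency tables of". That list holds serious TEAEs (overall, by descending frequency, related, and Grade 3 or 4). SAP 5.1 defines a frequency summary as number and percentage, so these tables have no time denominator.

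After the list, the section adds that "the incidence rate per 100 person-years will be summarized for all TEAEs and Grade 3 or 4 TEAEs by system organ class", preferred term and arm. The rate is 100n/T. A subject with the event contributes time to the first event; a subject without it contributes time until death or 28 days past the last dose, whichever is first. Elsewhere in SAP 12, exposure-adjusted rates are planned for dose-escalated subjects (end of 12.1) and for events of special interest (12.2.1). Serious events as a class have none.

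The main definition of TEAEs is "adverse events that started between the first dose date and 28 days after the last dose date of study treatment". Protocol 8.2.1 lets dosing continue while the subject benefits. Protocol 12 stops it at relapse with more than 15% blasts, among other reasons. Protocol 11.1 counts as an adverse event "any clinically significant adverse change in the frequency or intensity of a pre-existing condition including AML relapse".

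**The concern.** The length of the TEAE window is set by time on treatment, and time on treatment depends partly on relapse, which azacitidine is meant to delay. If it succeeds, azacitidine subjects are observed for serious TEAEs for longer. The same risk per unit of time then gives a higher crude percentage on azacitidine.

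The SAP recognises this for the broader categories by giving them rates, and then leaves out the seriousness category. At stake is how the serious-TEAE comparison reads: part of an apparent excess on azacitidine could be exposure alone, and no planned table would separate the two. That exposure will differ is an inference from the design; neither document gives an expected duration by arm.

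**Working it through.** The plan states no figure on this point, so there is nothing to reproduce. The check is a text comparison and then an illustration of size.

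**Text.** Reading SAP 12 to 12.3 and Protocol 10.7 together, no section commits to a person-year rate for serious TEAEs. The all-TEAE rate includes them but does not separate them. The person-years in SAP 9.1 run to 14 days after the last dose (or death), not 28, and do not stop at a first event. A reader therefore cannot rebuild the 12.1-type serious rate from them. The by-cycle tables of first occurrence are listed for TEAEs overall, not for serious ones.

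**Inputs, all assumed.** Placebo mean time on treatment m = 0.5, 0.75 or 1.0 years, exponentially distributed. Azacitidine mean = k·m. The value k = 1.43 borrows the planned ratio of OS medians, 22.9/16; k = 1.2 is a milder case. Serious-event hazard r = 0.3, 0.5 or 1.0 per person-year, the same in both arms. From SAP 12.1, d = 28/365.25 = 0.0767 years after the last dose.

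**Constant hazard.** P(at least one event) = 1 − exp(−r·d)/(1 + r·m).

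- r = 0.3, m = 0.5: placebo 1 − 0.9773/1.15 = 15.0%; azacitidine (mean 0.715) 1 − 0.9773/1.2145 = 19.5%; excess 4.5 points.
- r = 1.0, m = 0.75: placebo 1 − 0.9262/1.75 = 47.1%; azacitidine (mean 1.0725) 1 − 0.9262/2.0725 = 55.3%; excess 8.2 points.

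Crude excess on azacitidine in percentage points, k = 1.43:

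| r | m = 0.5 | m = 0.75 | m = 1.0 |
|---|---|---|---|
| 0.3 | 4.5 | 5.8 | 6.8 |
| 0.5 | 6.1 | 7.3 | 8.0 |
| 1.0 | 7.7 | 8.2 | 8.2 |

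At k = 1.2 the excess is 2.2 to 4.2 points; at k = 1.0 it is zero. The person-year rate equals r in both arms, so its ratio is 1.00.

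**When the hazard is not constant.** The risk remains equal and k = 1.43; ratios are azacitidine to placebo.

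| Pattern of events | Crude ratio | Rate ratio |
|---|---|---|
| Constant, as above | 1.15–1.30 | 1.00 |
| Front-loaded: 1.0–2.0 per person-year for 56 days, then 0.3–0.5 | 1.11–1.20 | 0.86–0.97 |
| Constant, plus a 10–20% chance in the 28 days after stopping | 1.10–1.19 | 0.85–0.98 |
| Only in the 28 days after stopping | 1.00 | 0.71–0.73 |
| Rising: 0.3, then 1.0 after 6 months | 1.25–1.38 | 1.07–1.12 |
| 0.05 per person-year plus 10% after stopping, 9-month mean, data cut at 1 year | 0.92 | 0.80 |

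For the third row, let q be the chance of an event at a uniform time in the 28 days after stopping, and S0 = 1/(1 + r·m). Events per subject = r·m·S0 + S0·[1 − (1 − q)·exp(−r·d)]. Person-time = m·S0 + S0 × the integral from 0 to d of (1 − q·u/d)·exp(−r·u) du. With r = 0.5, q = 20%, m = 0.75, placebo has S0 = 0.7273, events 0.2727 + 0.7273 × 0.2301 = 44.0% and 74.0 per 100 person-years. Azacitidine has 49.9% and 67.2 per 100 person-years.

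**The case against.** The strongest reply is that much is already covered and that the extra rate is not neutral.

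**Coverage.** Grade 3 or 4 TEAEs and special-interest events have rates, and many serious events will be among them. Treatment duration is reported by arm. SAP 11.3.2 plans cumulative-incidence curves for discontinuation with adverse events and death as separate causes, and Protocol 10.7 adds Kaplan-Meier for discontinuation due to adverse events. SAP 12.1 has an alternative TEAE window that closes when subsequent AML therapy starts, and it permits further safety analyses. Protocol 10.7 names no person-year rates, so the SAP already goes beyond it. This keeps the point minor but does not close it. Seriousness is defined by outcome, not grade (Protocol 11.2.1 and 11.2.2), so a Grade 3 or 4 rate is only a partial substitute. Discontinuation curves count only events that end treatment. A permission to add analyses commits to nothing.

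**Non-neutrality.** This stands. Relapse is an adverse event and, above the blast threshold, ends treatment, so some serious events may cluster at stopping. The rate then leans towards azacitidine; when events occur only at stopping, the crude figure is right and the rate is the biased one. A reader might infer that showing both figures brackets the truth. It need not: under a rising hazard both ratios exceed 1, and with stop-clustered events and a 1-year data cut both fall below 1. The rate adds information only if its assumption is stated beside it.

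**Deaths.** A reader might also infer that fatal TEAEs need the same repair. The documents do not support that as a material gap. SAP 11.2.1 says "Kaplan Meier methods will also be used to estimate the death probabilities at 30, 90 days, 6 months and 1 year", and SAP 12.3 says "A summary of all deaths will be provided by treatment period" and by cause. A fatal-TEAE rate would be supportive at most.

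**Conclusion.** The point holds for serious TEAEs. They are the one major safety category that SAP 12.1 leaves to crude percentages with no close time-based counterpart elsewhere in the plan. With equal risk and k = 1.43, the crude excess on azacitidine is 4.5 to 8.2 points under a constant hazard. It is 2.2 to 4.2 points at k = 1.2 and zero if exposure is equal. Exposure, hazard and ratio are all assumptions. OS and RFS inference is untouched.

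Two stronger readings fail. The plan does not ignore exposure in its safety analysis; it gives rates to several categories. Nor does the Grade 3 or 4 label conceal fatal events. It follows Protocol 10.7, which names "AEs classified as CTCAE (Version 4.0) Grade 3 or Grade 4". It is true that in severity summaries "subjects with multiple events at the preferred term level will be counted once and for the highest reported severity", so a subject whose event reaches Grade 5 under the same term could leave a Grade 3 or 4 row if that rule governs it. But the maximum-severity and leading-to-death tables still show that subject, so a separate Grade 3-or-higher row is not needed.

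**What to change.** In SAP 12.1, extend the rate sentence to cover *all TEAEs, serious TEAEs, and Grade 3 or 4 TEAEs*, with the time rule already given there. Place the serious rate next to the crude serious table and a first-occurrence-by-cycle table run for serious TEAEs, since the planned one covers all TEAEs. Add a footnote that the rate assumes a roughly constant hazard and can favour the longer-exposed arm when events cluster early or at treatment stop.

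The cost is one sentence, one footnote and a few reruns of existing table programs on data already collected. The downside is a few more tables and a rate that can itself mislead, with ratios of 0.85 to 0.98 or, at the extreme, 0.71 to 0.73 under equal risk in the stop-clustered cases above. The rate should therefore accompany the crude table and not replace it.
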